2. TRIAL OBJECTIVES AND ENDPOINTS

2.1 MAIN OBJECTIVES, PRIMARY AND SECONDARY ENDPOINTS

2.1.1 Main objectives

A key objective of this trial is to explore the efficacy of 3 doses (20 mg, 40 mg, and 80 mg) of BI 764198 with respect to their effect in lowering proteinuria. The primary endpoint is the proportion of patients achieving at least 25% reduction in 24-hour urine protein creatinine ratio (UPCR) relative to baseline at week 12 in patients with primary FSGS, and patients with monogenic FSGS as a result of TRPC6 mutations causing FSGS. Additional objectives in this study are to investigate the safety, tolerability, and pharmacokinetic and pharmacodynamic profiles of BI 764198 vs placebo.

The primary treatment comparison will be while on treatment, including all data prior to early discontinuation or lost to follow-up.

2.1.2 Primary endpoint

The primary endpoint is patients achieving at least 25% reduction in 24-hour urine protein-creatinine ratio (UPCR) relative to baseline at week 12. For details on efficacy assessments and definition of baseline, see section [5.1.1](#).

2.1.3 Secondary endpoints

[figure not shown]
The secondary endpoints are:

- Change in 24-hour UPCR relative to visit 3 at week 12
- Change in 24-hour UPCR relative to baseline at week 13
- Change in 24-hour urinary protein excretion relative to baseline at week 12
- The following pharmacokinetic parameters of BI 764198 will be determined if feasible:
 - Steady state trough concentration $C_{pre,ss}$ on week 4 and week 12

For details on efficacy assessments and definition of baseline, see section [5.1.1](#).

[figure not shown]
Clinical Trial Protocol

Proprietary confidential information © 2025 Boehringer Ingelheim International GmbH or one or more of its affiliated companies

2.2.2.2 Safety endpoints

- AEs (including clinically relevant findings from the physical examinations)
- SAEs occurring during the course of the study
- AEs leading to treatment discontinuation
- Vital signs (blood pressure, pulse rate)
- Safety laboratory tests
- 12-lead ECG
- Ophthalmological assessments

Clinical Trial Protocol

Proprietary confidential information © 2025 Boehringer Ingelheim International GmbH or one or more of its affiliated companies

[figure not shown]
3. DESCRIPTION OF DESIGN AND TRIAL POPULATION

3.1 OVERALL TRIAL DESIGN

This multicenter, randomized, double-blind, parallel group study will assess 3 doses of BI 764198 compared to placebo administered orally once daily for 12 weeks in patients with primary or TRPC6 monogenic FSGS.

After completion of all the screening procedures, eligible patients will be randomized into one of the 4 treatment groups stratified by use of corticosteroids, and treated for 12 weeks. It is planned to randomize approximately 15 patients in each treatment group. At the end of the treatment period, there will be a follow-up visit at day 7 after end of treatment. A 2nd follow-up visit will be scheduled via telephone, 30 days from end of treatment. Eye exams (section [5.2.5.1](#)) will be completed at the 2nd follow-up visit. A schematic illustration of the trial design is presented in Figure 3.1: 1.

Figure 3.1: 1 Study design

3.2 DISCUSSION OF TRIAL DESIGN, INCLUDING THE CHOICE OF CONTROL GROUP

A randomized, double-blind, placebo-controlled design is selected for this study. It is standard in studies at this early stage of development to use placebo as a control group in order to evaluate efficacy, safety and tolerability. The conduct of this short duration proof of clinical principle study will be on top of an array of established standard of care modalities including conservative management and steroid-based immunosuppression regimens.

Most FSGS studies on glomerular diseases have used different metrics of proteinuria including UPCR. UPCR will be measured from 24-hour urine in this study.

Clinical Trial Protocol

Proprietary confidential information © 2025 Boehringer Ingelheim International GmbH or one or more of its affiliated companies

UPCR reduction ratio (follow-up vs. baseline) for Cyclosporine A (CSA) and mycophenolate mofetil/dexamethasone (MMF/DEX) in a study with adults and children with steroid-resistant FSGS was analyzed ([P11-13071](#)). At week 8, there were approximately 65% and 50% reduction of UPCR for CSA and MMF/DEX, respectively. A 12-week treatment to identify a reduction in UPCR should therefore be sufficient to demonstrate efficacy in the study. In addition, efficacy will further be assessed in this study by the evaluation of [REDACTED] 24-hour proteinuria as secondary endpoints.

3.3 SELECTION OF TRIAL POPULATION

This study will randomize approximately 60 patients with primary FSGS or with TRPC6 mutations causing FSGS. It is planned to conduct the study in approximately 55 sites in multiple countries. A sufficient number of patients will be screened to meet the randomization goal.

Study sites in selected countries will have the option of integrating a decentralized clinical trial (DCT) model where the study visits are conducted outside of a dedicated healthcare or research facility. This would allow patients to participate in the trial remotely and complete the study in their own home or residence. The DCT model can bring the clinical trial to patient's homes through telemedicine, a smartphone device, and through the deployment of mobile research nurses (MRN). The MRN will visit the patient's home and complete trial procedures in collaboration with the site principal investigator and study staff.

Sites participating in the DCT model would also continue to enroll patients using the traditional site-based approach where the patient visits the clinic at the specified time points in the protocol. Sites with DCT integration can also allow active ongoing patients in the trial to switch to remote participation. Additional operational guidelines will be provided in a separate DCT operational manual. A copy of the operational manual will be provided in the ISF.

Recruitment of patients for this trial is competitive, i.e. screening for the trial will stop at all sites at the same time once a sufficient number of patients has been screened. Investigators will be notified about screening completion and will then not be allowed to screen additional patients for this trial. Patients already in screening at this time may be allowed to continue to randomization if eligible.

A log of all patients enrolled into the trial (i.e. who have signed informed consent including patients who signed a screening consent or provided verbal consent) will be maintained in the ISF irrespective of whether they have been treated with investigational drug or not. If retrospectively it is found that a patient has been randomized in error (did not meet all inclusion criteria or met one or more exclusion criteria), the sponsor or delegate should be contacted immediately. Based on individual benefit-risk assessment, a decision will be made whether continued trial participation is possible.

Clinical Trial Protocol

3.3.1 Main diagnosis for trial entry

The study will include patients with primary FSGS, and patients with monogenic FSGS as a result of TRPC6 mutations.

Refer to section [8.3.1](#) for the documentation requirements pertaining to the inclusion and exclusion criteria.

3.3.2 Inclusion criteria

1. Signed and dated informed consent in accordance with ICH-GCP and local legislation prior to admission to the study.
2. Male and female patients 18 years to 75 years (both inclusive) of age on the day of signing informed consent.
3. Patients diagnosed with biopsy proven primary FSGS or documented TRPC6 gene mutation causing FSGS prior to screening visit.
4. UPCR ≥ 1000 mg/g based on first morning void urine sample during screening.
5. *Inclusion criterion 5 removed in global amendment 2. Numbering of subsequent criteria was not changed.*
6. Patients treated with corticosteroids must be on a stable dose for at least 4 weeks prior to screening visit with no plan to change the dose until end of trial treatment.
7. Patients treated with ACE inhibitors, ARBs, finerenone, aldosterone inhibitors, or SGLT2 inhibitors should be on a stable dose for at least 4 weeks prior to screening visit with no plan to change the dose until end of trial treatment.
8. Body Mass Index (BMI) of ≤ 40 kg/m² at screening visit.
9. Women of childbearing potential (WOCBP¹) must be willing and able to use highly effective methods of birth control per ICH M3 (R2) that result in a low failure rate of less than 1% per year when used consistently and correctly. A list of contraception methods meeting these criteria is provided in the informed consent form (ICF) and in section [4.2.2.3](#).

3.3.3 Exclusion criteria

1. Known monogenic (with the exception of TRPC6 gene mutations) or clinical or histologic evidence of secondary FSGS.
2. Documented Alport syndrome, Nail Patella syndrome, diabetic nephropathy, IgA-nephropathy, lupus nephritis, or monoclonal gammopathy (e.g., multiple myeloma).
3. Genito-urinary malformations with vesicoureteral reflux or renal dysplasia.
4. A history of organ transplantation or planned transplantation during the course of the study.

¹ A woman is considered of childbearing potential (WOCBP), i.e. fertile, following menarche and until becoming post-menopausal unless permanently sterile. Permanent sterilisation methods include hysterectomy, bilateral salpingectomy and bilateral oophorectomy. Tubal ligation is NOT a method of permanent sterilisation. A postmenopausal state is defined as no menses for 1 year without an alternative medical cause.

Clinical Trial Protocol

Proprietary confidential information © 2025 Boehringer Ingelheim International GmbH or one or more of its affiliated companies

5. Uncontrolled hypertension defined as an average resting systolic blood pressure >160 mmHg calculated from the last two of the triplicate sitting blood pressure measurements at screening visit. Patients with a documented history of white coat hypertension may be included.
6. Concomitant use of calcineurin inhibitors within 5 half-lives before screening visit.
7. Concomitant treatment with cytotoxic agents (cyclophosphamide, chlorambucil), or CD20 monoclonal antibody, e.g., rituximab, within 5 half-lives before screening visit.
Note: use of other immunosuppression therapies considered as standard of care may be allowed as long as the patient remains on stable dose throughout the study.
8. Treatment with metformin or dofetilide (MATE1 or OCT2 substrates); dabigatran or digoxin (P-gp substrates with narrow therapeutic window) within 5 half-lives before screening visit.
9. Treatment with strong inhibitors or strong inducers of CYP3A within 1 week or 5 half-lives before screening visit (whichever is longer).
10. Estimated glomerular filtration rate (eGFR) < 30 mL/min/1.73 m² (CKD-EPI formula based on serum creatinine and cystatin C) at screening visit.
11. Alanine aminotransferase (ALT)/aspartate aminotransferase (AST) >3X the upper limit of normal (ULN) at screening visit.
12. Clinically significant laboratory abnormalities or medical conditions which pose a safety risk for the patient or may interfere with the trial objectives in the investigator's opinion (except for renal function tests or deviation of clinical laboratory values that are related to FSGS) at screening visit.
13. QTc intervals (QTcF) greater than 450 ms in males or greater than 470 ms in females, or any other clinically relevant ECG findings (at the investigator's discretion) at screening visit.
14. History of congenital long QT syndrome, previous drug-induced QT prolongation, or other risk factors for Torsade de pointes (e.g. hypokalemia, bradycardia, heart failure).
15. Detection of graded cataract by LOCS III higher than NC1/NO1, C0, P0 in the slit lamp eye examination at screening visit. Planned cataract surgery during participation in the study. Patients with cataract who have undergone lens replacement are not excluded.
16. A history of gastrointestinal (GI) surgery or GI disorders that could interfere with absorption of trial medication in the investigator's opinion.
17. Major surgery (major according to the investigator's assessment, e.g. hip replacement) performed 3 months before the screening visit or planned within 6 months after entering the study.
18. Any documented active or suspected malignancy or history of malignancy within 5 years prior to screening visit, except appropriately treated basal cell carcinoma of the skin or in situ carcinoma of uterine cervix.
19. History of relevant allergy or hypersensitivity according to the investigator's clinical judgment (e.g. systemic hypersensitivity reactions including anaphylaxis and anaphylactoid reactions to the excipients or any other systemically administered agent).
20. Patients who need to use restricted medications (section [4.2.2.1](#)) or any drug considered likely to interfere with the safe conduct of the study, e.g. drugs with known QT-prolongation effects.

Clinical Trial Protocol

Proprietary confidential information © 2025 Boehringer Ingelheim International GmbH or one or more of its affiliated companies

21. Patients not expected to comply with the protocol requirements or not expected to complete the study as scheduled (e.g. chronic alcohol or drug abuse or any other condition that, in the investigator's opinion, makes the patient an unreliable study participant).
22. Previous enrollment in this trial, or currently enrolled in another study investigating a device or drug, or less than 30 days or 5 times half-life of the investigational drug (whichever is longer) since ending another investigational drug study. Patients participating in observational studies will not be excluded.
23. Women who are pregnant, nursing, or who plan to become pregnant while in the study.
24. A positive test for SARS-CoV-2 during the screening period and up to the randomization.

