Proprietary confidential information © 2025 Boehringer Ingelheim International GmbH or one or more of its affiliated companies

	
Estimated glomerular filtration rate (eGFR) < 30 mL/min/1.73 m² (CKD-EPI formula based on serum creatinine and cystatin C) at screening visit.QTc intervals (QTcF) greater than 450 ms in males or greater than 470 ms in females, or any other clinically relevant ECG findings (at the investigator's discretion) at screening visit.
Test product	BI 764198
dose	20 mg, 40 mg, 80 mg, and matching placebo, q.d.
mode of administration	Oral (p.o)
Comparator products	Matching placebo to BI 764198
dose	Not applicable
mode of administration	Oral (p.o)
Duration of treatment	12 weeks
Statistical methods	For the primary analysis, descriptive statistics will be provided. Proportion of patients achieving at least 25% UPCR reduction relative to baseline at 12 weeks will be described. In addition, an ANOVA model for the UPCR change from baseline at 12 weeks (and other endpoints as applicable) will be used to see difference across arms. The dose-response relationship based on reduction in log of UPCR will be explored using a graphical approach.

Clinical Trial Protocol

Proprietary confidential information © 2025 Boehringer Ingelheim International GmbH or one or more of its affiliated companies

FLOW CHART A – STUDY PROCEDURES

Trial Periods	Screening	Treatment Period						Follow-up
		1	2	3	4	5	EoT ²	
Visit ¹		1	2	3	4	5	EoT ²	FUP1
Week			0		4	8	12	13
Days from first dose	-30 ⁴	1 ⁵	4	29	57	85	92	115
Time window for visits (days)		0	+3	±3	±3	±3	±2	±3
Informed consent ⁶	X							
Demographics	X							
Height ⁷ , body weight	X			X	X	X	X	
Medical history	X	X						
Review of inclusion /exclusion criteria	X	X						
Physical exam ⁸	X			X		X		
Vital signs	X ²⁸	X	X	X	X	X	X	
12-lead ECG ⁹	X	X	X	X	X	X	X	
Sampling for safety laboratory (incl. serum creatinine/cystatin C for eGFR)	X	X	X	X	X	X	X	
Pregnancy testing ¹⁰	X	X		X	X	X	X	
Eye exams ¹¹	X					X ¹²		X ¹²
First morning void (FMV)	X							

Clinical Trial Protocol

Proprietary confidential information © 2025 Boehringer Ingelheim International GmbH or one or more of its affiliated companies

FLOW CHART A – STUDY PROCEDURES (cont.)

Trial Periods	Screening	Treatment Period						Follow-up
		2	3	4	5	EoT ²	FUP1	
Visit ¹	1							
Week		0		4	8	12	13	
Days from first dose	-30 ⁴	1 ⁵	4	29	57	85	92	115
Time window for visits (days)		0	+3	±3	±3	±3	±2	±3

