- To monitor for ocular changes, eye exams at screening, end of treatment, and 30 days after last dose of trial medication will be performed. Patients diagnosed with cataract (Lens Opacities Classification System III (LOCS III) higher than NC1/NO1, C0, P0 ([R99-2093](#)) in slit lamp eye examination will be excluded from the study at screening, and if diagnosed after inclusion in study will be discontinued from study treatment.
- To monitor for renal function, serum cystatin C and serum creatinine levels will be assessed at regular intervals and GFR estimation will be based on cystatin C values.
- There are no risks expected by stopping the study drug during the course of the trial.
- During the study, patients will be monitored for AEs.
- Females of childbearing potential who are pregnant, breast-feeding or intend to become pregnant or are not using an adequate contraceptive method throughout the trial and until 5 days after the last dose of the trial medication are excluded from the trial (section [4.2.2.3](#)).
- Set up of an internal study safety review committee who will review unblinded data periodically to allow continuous assessment of drug exposure, efficacy, and safety. The safety review committee will include a cardiologist and an ophthalmologist. For more information, see section [8.7](#).

Patient participation in this trial will be consistent with local public health guidance and regulations. During screening, patients with symptoms of COVID-19 or a confirmed severe acute respiratory syndrome coronavirus 2 (SARS-CoV-2) infection will be excluded from participation in the trial. During participation in the study, if a patient is diagnosed with COVID-19, trial treatment will be terminated in cases where the patient has severe illness (for example patients who require hospitalization, need supplemental oxygen, have compromised lung function, etc.) and patients will be discontinued from the study. If a patient has a mild SARS-CoV-2 infection, continuation of trial treatment will be at the discretion of the investigator. The investigator will make an individual benefit-risk assessment on a case-by-case basis considering all aspects and decide if the patient should continue treatment or discontinue treatment temporarily or permanently. There are no restrictions for trial participant to receive vaccination for COVID-19 during or after the study period.

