3.3.4.1 Discontinuation of trial treatment

An individual patient will discontinue trial treatment if:

- The patient wants to discontinue trial treatment. The patient will be asked to explain the reasons but has the right to refuse to answer.
- The patient has repeatedly shown to be non-compliant with important trial procedures and, in the opinion of both, the investigator and sponsor representative, the safety of the patient cannot be guaranteed as he/she is not willing or able to adhere to the trial requirements in the future.
- The patient needs to take concomitant medication which may increase their risk of adverse effects or interfere with the investigational medicinal product (section [4.2.2](#)). In cases where treatment is expected to be temporary (short course), the case should be discussed with the sponsor and a decision will be made on potentially restarting trial medication.
- The patient can no longer receive trial treatment for medical reasons (such as surgery, serious or severe drug induced liver injury attributable to the trial drug (section [5.2.6.1.4](#)), other AEs, other diseases, or pregnancy).
- The patient experiences confirmed QT prolongation of QTcF intervals greater than 500 ms or an increase of >60 ms compared to baseline (defined as visit 2, pre-dose measurement).
- The patient experiences clinically relevant conduction disorders (e.g. AV block \geq 2nd degree, bundle branch block).

Clinical Trial Protocol

Proprietary confidential information © 2025 Boehringer Ingelheim International GmbH or one or more of its affiliated companies

- The patient is diagnosed with cataract (graded by LOCS III higher than NC1/NO1, C0, P0) during study treatment.
- eGFR below 25 mL/min/1.73 m² (CKD-EPI formula based on serum cystatin C) and not improved by resolution of transient events (e.g. dehydration).
Patient experiences acute kidney injury as per clinical judgement by the investigator and/or according to the modified Kidney Disease: Improving Global Outcomes (KDIGO) definition ([R17-2439](#)) and adapted for cystatin C as opposed to serum creatinine ([R14-1203](#), [R15-5270](#)).
 - Increase in cystatin C to \geq 1.5 times the baseline value, which is known or presumed to have occurred within the prior 7 days.

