5.2.3 Safety laboratory parameters

Safety laboratory parameters to be assessed are listed in Table [5.2.3: 1](#). Sampling time points are provided in the Flow Chart A.

All analyses will be performed by a central laboratory, and the respective reference ranges will be provided in the laboratory manual. Instructions regarding sample collection, sample handling, processing, and shipping are provided in the laboratory manual.

If central lab services or the lab kits provided by the central lab are not available at the study site, safety labs may be done at a local lab. The results of the lab tests should be entered in the eCRF. Please note the local labs should be used only if it becomes necessary, and the CT Manager should be informed.

For patients participating in the trial remotely via the DCT model, laboratory kits will be made available at the patient's home for the respective visits. The MRN will collect, process, and ship lab samples to the central laboratory or the study site (when applicable). Additional information will be provided in the DCT operations manual.

Patients do not have to be fasted for the blood sampling for the safety laboratory.

Clinical Trial Protocol

Proprietary confidential information © 2025 Boehringer Ingelheim International GmbH or one or more of its affiliated companies

The central laboratory will send laboratory reports to the investigator. It is the responsibility of the investigator to evaluate the reports. Clinically relevant abnormal findings as judged by the investigator will be reported as AEs (refer to section [5.2.6](#)).

In case the criteria for hepatic injury are fulfilled, a number of additional measures will be performed (section [5.2.6.1](#) and the DILI Checklist provided in the electronic data capture (EDC) system. The amount of blood taken from the patient concerned will be increased due to this additional sampling for DILI assessments. The central laboratory will transfer the data to the sponsor periodically.

For assessment of eGFR exclusion criterion (section [3.3.3](#)), the CKD-EPI formula based on serum creatinine and serum cystatin C will be used. The serum cystatin C-based CKD-EPI formula will be used for the calculation of eGFR in the evaluation of efficacy. [REDACTED]

[REDACTED].

Clinical Trial Protocol

Proprietary confidential information © 2025 Boehringer Ingelheim International GmbH or one or more of its affiliated companies

Table 5.2.3: 1 Safety laboratory tests

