Proprietary confidential information © 2025 Boehringer Ingelheim International GmbH or one or more of its affiliated companies

1. If initial CK is elevated, re-test CK with CK-MB and troponin I.
2. Reported to the investigator only up to visit 2.
3. eGFR based on serum creatinine and cystatin C will be reported to the investigator only up to visit 2.
4. eGFR based on serum cystatin C will be reported to the investigator from visit 2 onwards.
5. Only at screening visit.

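### Entry is judged on the combined eGFR and stopping on the cystatin C-only eGFR, so a patient can be randomized while already below the numeric stopping limit

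*Protocol*

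**What the plan says.** **Entry.** Exclusion 10 (Protocol 3.3.3) sets a limit of 30 mL/min/1.73 m² on the "CKD-EPI formula based on serum creatinine and cystatin C) at screening visit". Section 5.2.3 confirms that for this criterion "the CKD-EPI formula based on serum creatinine and serum cystatin C will be used".

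**Stopping.** Section 3.3.4.1 stops treatment at an eGFR below 25 ("CKD-EPI formula based on serum cystatin C) and not improved by resolution of transient events"). Section 1.4.2 says that for renal monitoring "GFR estimation will be based on cystatin C values". Section 1.2 gives the reason: the drug may raise serum creatinine by blocking its tubular secretion, without a change in kidney function.

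**Reporting.** Table 5.2.3: 1, footnote 4: "eGFR based on serum cystatin C will be reported to the investigator from visit 2 onwards". Footnote 3 reports the combined eGFR only up to visit 2. Cystatin C itself carries no reporting restriction.

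**Timing.** Randomization is at least seven days before visit 2, and the first dose is given at visit 2 (Flow Chart A footnote 23; section 4.1.4).

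**Other criteria.** Exclusion 12, on clinically significant laboratory abnormalities, applies "except for renal function tests or deviation of clinical laboratory values that are related to FSGS) at screening visit". Exclusion 21 is discretionary: "Patients not expected to comply with the protocol requirements or not expected to complete the study as scheduled".

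**The concern.** The 30 and the 25 look like an entry limit with a 5-unit margin above the stopping limit. They lie on different scales, so the margin is not guaranteed. A patient whose creatinine suggests better kidney function than their cystatin C can pass at 30 on the combined value while the cystatin C-only value is already below 25. The value that would show this is not scheduled to reach the investigator until after randomization. Visit 2 requires the investigator to look at the ECG before dosing (section 5.2.4) but sets no such requirement for eGFR.

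If the low value is stable, treatment ends because of the patient's state at entry and not because of a change on drug. The patient has then been exposed for no purpose, in a group where exposure is higher (section 1.2 reports AUC up 78% in severe renal impairment after a single 40 mg dose). The stop is an early discontinuation, which is an intercurrent event. Under SAP 7.4.1, UPCR measured after it is left out of the primary analysis, and a missing week-12 value counts as non-response. The patient still completes EoT, FUP1 and EoS and contributes safety and PK data.

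**Working it through.** The plan gives no figure of its own on this point, so there is nothing to reproduce. The check has four parts.

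**1. Order of events**

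| Step | Time | eGFR that governs or is reported |
|---|---|---|
| Entry check | Screening | Combined, limit 30 |
| Randomization | At least 7 days before visit 2 | No further check |
| First dose | Visit 2 | Cystatin C-only first reported from here |
| Stopping rule | On treatment | Cystatin C-only, limit 25 |

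Analyses are done by a central laboratory and no turnaround is stated. That the first dose precedes the visit 2 result is therefore an inference.

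**2. Can the two limits overlap?** The CKD-EPI equations are not in the documents. Assume that the combined value is a geometric blend with cystatin C weight w:

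combined = cr^(1−w) × cys^w

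Set combined = 30 and cys = 25, and solve cr = (30 / 25^w)^(1/(1−w)):

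- w = 0.3: cr = 32.4
- w = 0.5: cr = 30²/25 = 36.0
- w = 0.7: cr = 45.9

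A patient with a cystatin C-only eGFR just under 25 passes entry once the creatinine eGFR reaches about 32, 36 or 46, a gap between the markers of about 7, 11 or 21 units.

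**3. How many patients?** The documents give neither the eGFR distribution nor the spread between the markers, so everything here is assumed. Let D = ln(cys/cr) be normal with mean μ and standard deviation s, whatever the combined value C. The blend gives ln cys = ln C + (1−w)D, so

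P(cys < T) = Φ{[ln(T/C)/(1−w) − μ]/s}.

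Average over C uniform on 30–100 or 30–60, and multiply by 60. The grid is w = 0.3, 0.5, 0.7; s = 0.2, 0.3, 0.4; μ = −0.2, 0, +0.2 (cystatin C eGFR 18% lower, equal or 22% higher): 3 × 3 × 3 × 2 = 54 settings.

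One point worked: w = 0.5, μ = 0, s = 0.3, C = 30 gives ln(25/30) = −0.182, divided by 0.5 = −0.365, divided by 0.3 = −1.22, so P = 0.11. At C = 40 it is below 0.001. The risk lies almost wholly with patients just above the entry limit. Averaged over 30–100 this setting gives 0.22 patients per 60; over 30–60, 0.52.

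Expected patients per 60 below 25 at entry, over the 54 settings:

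- median 0.22, quartiles 0.03 and 0.97, range below 0.01 to 6.5
- one or fewer in 40 settings: 9 of 18 with the lower shift, 14 of 18 unshifted, 17 of 18 with the higher shift
- the maximum needs w = 0.3, s = 0.4, the lower shift and all 60 patients at 30–60 together

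These counts overstate stops, because the transient-event condition is not modelled.

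**4. What does one stop cost the primary endpoint?** With 15 per arm and the responder rates assumed in Protocol 7.5, turning one expected outcome into a non-response lowers the expected arm rate by 0.09/15 = 0.6 points (placebo) to 0.40/15 = 2.7 points (80 mg). The exact 95% interval for 6 of 15 runs from 16% to 68%.

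**The case against.** The choice of scales is deliberate and defensible. Before dosing, creatinine carries no drug effect, so both markers can be used; on drug, creatinine may mislead, so cystatin C is used alone. Raw cystatin C is not withheld, eligibility is reviewed again at visit 2, and exclusion 21 leaves room for judgement. The stopping rule is softened by its transient-event clause. Samples at visit 2 and day 4 would show a stable low value early. Text is redacted in 5.2.3 just after the formulas are named, and the central-laboratory specifications are not available. The frequency rests entirely on assumptions. The fix also does little: it removes a median of 0.22 patients per 60 and leaves a median of 2.0 with a cystatin C-only eGFR of 25–30, who may stop after a small decline.

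Much of this stands, and it fixes the priority: frequency is unknown and probably low, exposure is probably short, and the gain is small. It does not close the gap. The reason for using cystatin C on treatment does not explain the absence of a check on that scale at entry. A second eligibility review cannot apply a criterion that does not exist, and nothing requires an investigator to convert raw cystatin C or act on it. The exclusion list shows no redaction, and the redacted text in 5.2.3 follows a sentence about eGFR for efficacy. Elsewhere the protocol does align the two ends: cataract uses the same LOCS III cut-off for exclusion and for stopping.

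**Conclusion.** The concern holds. Entry and stopping use different eGFR scales, the stopping value is first reported from visit 2, and no mandatory criterion prevents randomizing someone already below 25 on that scale. That the overlap is possible follows from the text and needs only modest disagreement between the markers. Its size rests on the assumed blend, weights, spread, shift and eGFR range: most plausibly fewer than one patient in 60, with several only if every assumption is unfavourable. Discordance precedes randomization, so no arm is favoured, and the effect on any arm's responder rate is small beside its sampling error. The case for acting is patient protection at very low cost. Two facts remain unstated: the laboratory turnaround, and whether the laboratory already calculates the cystatin C-only eGFR at screening.

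**What to change.** Change footnote 4 of Table 5.2.3: 1 so that the cystatin C-only eGFR from the screening sample is calculated and reported to the investigator before randomization. Add to exclusion 10 that a patient whose screening cystatin C-only eGFR is below 25 mL/min/1.73 m² is not randomized, with one repeat if a transient cause is suspected, modelled on the single retest in section 6.2.1. Leave the on-treatment rule as it is.

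The floor of 25 is the protocol's own stopping value, so it bars only patients who already meet the numeric criterion. A floor of 30 would add a buffer but bar about 2 more patients per 60 (grid median) who need not stop.

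The cost is one sentence in exclusion 10 and a change to laboratory calculation and reporting. Flow Chart A already schedules the blood at screening ("Sampling for safety laboratory (incl. serum creatinine/cystatin C for eGFR"), so no new sample is needed apart from the optional repeat. The downside is that a few patients with discordant markers do not enter, and those just above 25 may still stop later.
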